3.4.7 Dose intensity

Dose intensity will be derived separately for the initial treatment period and the re-treatment period. Relative dose intensity (RDI) is the percentage of the actual dose intensity delivered relative to the intended dose intensity through to treatment discontinuation.

RDI will be defined as follows:

- $RDI = 100\% * d/D$, where d is the actual cumulative dose delivered up the actual last day of dosing and D is the intended cumulative dose up to the actual last day of dosing. D is the total dose that would be delivered, if there were no modification to dose or schedule. When accounting for the calculation of intended cumulative dose 3 days should be added to the date of last dose to reflect the protocol allowed window for dosing for all treatments

When deriving actual dose administered the volume before and after infusion will also be considered.

For the Study medication treatment, where the last dose is on the week 50 visit and if there are scans post week 50, the censoring of progression should occur at week 50 for the purposes of RDI.

Example of dose intensity for MEDI4736

Table 7 Dose intensity scenarios

RDI	Patient	Study Day										
		1	15	29	43	57	71	85	99	113		
100%	1	X	X	X	X	X	X	X	X	X	X	PD
100%	2	X	X	X	X	X	X	X	X	X[D]		PD
56%	3	X	X	X	X	X	O	X	X	X		PD
67%	4	X	X	O	X	X	X	O	X	O		PD

X: Dose of 10mg/kg taken; O: Dose missed; [D]: Dose discontinued; PD: Progressive Disease

Patients 1-4 progressed on Day 115, so the intended dose through to progression was $9 * 10\text{mg/kg}$ of MEDI4736 = 90mg/kg.

Patient 1 received a total of 90 mg/kg of MEDI4736, whereas other patients received less treatment due to:

- Early stopping prior to PD (Patient 2)

- Dosing delays (Patient 3)
- Missed doses (Patient 4)

The examples of Patients 2 and 4 illustrate that for RDI, the end of actual dosing period is calculated based on the smallest recovery period after the last non-zero dose.

Patient 1: $RDI = (9 * 10 \text{ mg/kg}) / 90 \text{ mg/kg} = 100\%$

Patient 2: $RDI = (8 * 10 \text{ mg/kg}) / 80 \text{ mg/kg} = 100\%$

Patient 3: $RDI = (5 * 10 \text{ mg/kg}) / 90 \text{ mg/kg} = 56\%$

Patient 4: $RDI = (6 * 10 \text{ mg/kg}) / 90 \text{ mg/m}^2 = 67\%$

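### SAP 3.4.7: the worked RDI for Patient 4 (67%) contradicts the last-dose rule it is said to illustrate, which gives 75%

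*SAP*

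**What the plan says.** SAP 3.4.7 opens by describing RDI as the percentage of the actual dose intensity delivered "relative to the intended dose intensity through to treatment discontinuation". It then gives a formula, RDI = 100% × d/D. Here d is the dose delivered up to the last day of dosing, and "D is the intended cumulative dose up to the actual last day of dosing". For the intended dose, "3 days should be added to the date of last dose to reflect the protocol allowed window for dosing for all treatments".

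Table 7 sets out four patients on a two-weekly schedule (Days 1, 15, 29, 43, 57, 71, 85, 99 and 113). The key reads "X: Dose of 10mg/kg taken; O: Dose missed", and Patient 4's row reads "67% 4 X X O X X X O X O". The text below the table begins "Patients 1-4 progressed on Day 115, so the intended dose through to progression was" and gives nine doses of 10 mg/kg, or 90 mg/kg.

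The section then cites Patients 2 and 4 as examples of its rule on where the dosing period stops: "the end of actual dosing period is calculated based on the smallest recovery period after the last non-zero dose". Patient 2 is worked as 80/80 = 100%. Patient 4 is worked as 60 mg/kg over 90 mg/m2 = 67%.

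**The concern.** One sentence names two patients as illustrations of the same rule, but their calculations use different denominators. Patient 2's stops at the last dose given. Patient 4's runs to progression, although that patient's last dose was also on Day 99.

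Worked examples in an SAP are there to settle how a definition is programmed. Here the example and the definition give different answers. RDI is a planned summary for the safety analysis set (SAP 4.2.11). Two programmers, one working from the definition and the other from the example, would report different values for any patient who missed the final scheduled dose or doses before progression or discontinuation.

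**Working it through.** **Inputs (all SAP 3.4.7 unless stated)**
- Planned dosing days: 1, 15, 29, 43, 57, 71, 85, 99, 113; 10 mg/kg each.
- Patient 4: doses given on Days 1, 15, 43, 57, 71 and 99 (six); missed on Days 29, 85 and 113. Last dose given: Day 99.
- Patient 2: eight doses given, taken from the text calculation; eight consecutive doses end on Day 99.
- Progression: Day 115.
- Window added to the last dose date for D: 3 days. For comparison, SAP 3.4.6 adds 13 days to the last dose date when it defines total exposure.

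**The SAP's own figure**

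Patient 4: 6 × 10 = 60 mg/kg delivered; 9 × 10 = 90 mg/kg intended through Day 115; 60/90 = 66.7%, printed as 67%. The division is right, but the denominator is the through-progression one.

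**The stated rule**

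Day 99 is planned dose number (99 − 1)/14 + 1 = 8, so D = 8 × 10 = 80 mg/kg. Adding 3 days gives Day 102, before the next planned dose on Day 113, so D stays at 80. RDI = 60/80 = 75%. The difference is 75.0 − 66.7 = 8.3 percentage points.

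**Does the result depend on where the period ends?**

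| End of period | Day | Planned doses | Patient 4 | Patient 2 |
|---|---|---|---|---|
| Last dose | 99 | 8 | 6/8 = 75% | 8/8 = 100% |
| Last dose + 3 days | 102 | 8 | 6/8 = 75% | 8/8 = 100% |
| Last dose + 13 days | 112 | 8 | 6/8 = 75% | 8/8 = 100% |
| Last dose + 14 days | 113 | 9 | 6/9 = 67% | 8/9 = 89% |
| Progression | 115 | 9 | 6/9 = 67% | 8/9 = 89% |

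Every period measured from the last dose that gives Patient 2 the printed 100% gives Patient 4 75%. Every one that gives Patient 4 the printed 67% gives Patient 2 89%.

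**Who is affected**

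Suppose n doses were planned up to the last one given, and m further scheduled doses were missed before progression. The through-progression denominator then multiplies RDI by n/(n + m). For Patient 4 this is 8/9, and 75% × 8/9 = 66.7%. When m = 0 the two denominators agree.

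**The case against.** The strongest defence rests on the opening definition, which runs to treatment discontinuation. Patient 2 is marked as discontinued and described as stopping before progression. Patient 4 carries no such mark and is described only as having missed doses. If Patient 4 is taken to have stayed on treatment until Day 115, that definition gives 80/80 = 100% and 60/90 = 67%, exactly as printed. The section also has a remark about censoring progression at Week 50 for RDI, so progression was in view when it was written, although that remark covers only patients whose last dose is at Week 50.

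This shows that the section contains two end points, and that part stands. It does not rescue the example. D is defined explicitly to the last day of dosing, and Patient 4 is named as an illustration of the last-non-zero-dose rule.

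A second objection is that the printed formula is not wrong taken alone: six doses with the last on Day 113 would give 67% under the rule. The finding does therefore rest on the final entry of Patient 4's row being a missed Day 113 dose. That row has nine entries for nine days, and its six doses match the text. Had the Day 113 dose been given, both denominators would be 90 and the example would illustrate nothing about the last non-zero dose.

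A reader might also infer that Patient 3 is miscalculated, because the row as it reads does not match the printed 56%. The documents do not support that conclusion. The dose counts in three of the four rows as they read disagree with the SAP's own calculations, so the table was probably damaged in conversion to text. Nothing is claimed about Patient 3.

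**Conclusion.** The inconsistency is real and minor. Under the definition of D and the rule that the example is said to show, Patient 4's RDI is 75%, not 67%. The result is the same with 0, 3 or 13 days added to the last dose date. It assumes that Patient 4's row is intact and that the explicit definition of D takes precedence over the looser opening phrase. The mg/m2 in the denominator is a separate unit slip, since dosing is in mg/kg.

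Following the example would understate RDI for patients who missed their final scheduled dose or doses. The documents give no basis for estimating how many there would be.

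A reader might go further and infer that the exposure table cannot be reproduced from the SAP. That does not follow. The d/D definition can be programmed without the examples, and the other items in SAP 4.2.11 (total and actual exposure, reasons for delays, number of infusions) do not use RDI. RDI is descriptive, so the co-primary analyses are untouched.

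**What to change.** Three changes to SAP 3.4.7:

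1. Correct Patient 4 to (6 × 10 mg/kg)/(80 mg/kg) = 75%, in Table 7 and in the text, with the unit in mg/kg.
2. Bring the opening phrase about treatment discontinuation into line with the definition of D, so that one end point applies throughout.
3. Keep the 90 mg/kg sentence, which is true of the schedule, but say that it describes planned dosing to Day 115 and is the RDI denominator only when the Day 113 dose was given.

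The cost is SAP wording. Data collection, dosing and trial conduct do not change.

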3.5 Pharmacokinetic and Immunogenicity Variables

Analyses to evaluate the pharmacokinetics and immunogenicity of MEDI4736 will be performed by AstraZeneca/MedImmune Clinical Pharmacology group or designee.

3.5.1 PK non-compartmental analysis

The actual sampling times will be used in the PK calculations. Pharmacokinetic concentration data and summary statistics will be tabulated. Individual and mean blood MEDI4736 concentration-time profiles will be generated. PK parameters will be determined using standard non-compartmental methods. The PK parameters will be determined after the first and steady state doses: peak and trough concentration (as data allow). Samples below the lower limit of quantification will be treated as missing in the analyses.

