#### **3.2.3.2 Dose justification**

Based on an analysis of the dose-escalation data from the ongoing FTIH study, a dose of 10 mg/kg Q2W administered for up to a maximum of 12 months is recommended for further development. This dosing regimen is expected to provide a level of PD-L1 inhibition that is predicted to result in a high probability of clinical response in the majority of patients.

This recommendation is supported by multiple lines of evidence including: in-vitro data, nonclinical activity, clinical PK-PDx, clinical biomarkers, and clinical activity data collected from the FTIH study. Based on the FTIH data, MEDI4736 exhibited non-linear (dose-dependent) PK consistent with target mediated drug disposition. A dose-dependent decrease in peripheral soluble PD-L1 was observed over the dose range of 0.1 to 10 mg/kg Q2W; consistent with engagement of MEDI4736 with PD-L1. Significant soluble PD-L1 (>90%) suppression at trough was observed with doses  $\geq 0.3$  mg/kg Q2W. PK parameters such as dose-normalised area under the drug concentration-time curve and  $t_{1/2}$  increased over the dose range of 0.1 to 10 mg/kg Q2W and approached linearity at 3 mg/kg Q2W; suggesting near complete target saturation (membrane bound and soluble PD-L1) with 3 mg/kg Q2W. The expected mean trough concentration following 3 mg/kg Q2W MEDI4736 is  $\sim 50$   $\mu\text{g/mL}$ . Although clinical activity has been observed at lower doses, and DLTs have not been observed at the highest dose studied (10 mg/kg Q2W), this dose/schedule is anticipated to maintain levels above a target median trough concentration (100  $\mu\text{g/mL}$ ). The target trough serum concentration of 100  $\mu\text{g/mL}$  accounts for the variability in PK ( $\sim 50\%$ ), PDx response and clinical activity (up to 100%) anticipated in a diverse cancer patient population and to maintain sufficient PK exposure in case of an ADA impact. The target serum concentration of

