100 µg/mL can be maintained with the 10 mg/kg Q2W dosing regimen. Data generated during the dose escalation phase of the FTIH study also suggest that higher doses (ie, 10 mg/kg Q2W) may be associated with better clinical activity while still providing an acceptable safety profile. Dose-related changes in a variety of peripheral biomarkers have been observed over the dose range of 0.1 to 3 mg/kg Q2W. Thus far, a low level of immunogenicity has been observed. Screening for ADA has detected 4 positive samples from 3 patients out of a total of 86 samples from 19 patients, with evidence for an impact on PK and target suppression in 1 individual. Thus, the clinical activity observed coupled with the safety profile, translational science correlates, and non-clinical data supports further development with a dose of 10 mg/kg Q2W.

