## **6.6 Pharmacokinetics and ADA**

### **6.6.1 Collection of PK samples and determination of drug concentration**

Blood samples (3.5 mL) for determination of MEDI4736 in serum will be taken at the times presented in the study plans in [Table 1](#) (Screening and the Treatment Period), [Table 2](#) (for follow-up of patients achieving disease control or who are discontinued due to toxicity or a reason other than confirmed PD) and [Table 3](#) (for follow-up of patients discontinuing due to confirmed PD). Patients receiving re-treatment after final DCO for the study will not undergo drug concentration or anti-drug antibody assessments.

Measurement of MEDI4736 concentrations in serum will be performed using a validated immunoassay. Samples for determination of MEDI4736 concentrations in serum will be analysed by a designated third party on behalf of AstraZeneca/MedImmune, using an electrochemiluminescence assay. The lower limit of quantification of MEDI4736 in serum is 50 ng/mL; however, this is dependent on the assay used.

Samples will be collected, labelled stored and shipped as detailed in Laboratory Manual. For blood volume see [Section 7.1](#).

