3.5.3 Immunogenicity analysis

Immunogenicity results will be analysed descriptively by summarizing the number and percentage of patients who develop detectable anti-MEDI4736 antibodies. The immunogenicity titre will be reported for samples confirmed positive for the presence of anti-MEDI4736 antibodies. Summaries will be based upon all patients from the safety population. The effect of immunogenicity on PK, PDx, efficacy and safety will be evaluated, but such analyses, if applicable, will be reported in a separate report.

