- For summaries at a patient level, all values should be included, regardless of whether they appear in a corresponding visit based summary, when deriving a patient level statistic such as a maximum.
- Baseline will be defined as the last non-missing measurement prior to the first dose of study treatment. For the re-treatment period baseline is similarly defined as the last non-missing measurement prior to the first dose on the re-treatment period. For laboratory data, any assessments made on day 1 will be considered pre-dose. If there are two visits equally eligible to assess patient status at baseline (e.g., screening and baseline assessments both on the same date prior to first dose with no washout or other intervention in the screening period) with assessment time missing, the average can be taken as a baseline value. For non-numeric laboratory tests (ie some of the urinalysis parameters) where taking an average is not possible then the best value would be taken as baseline as this is the most conservative. In the scenario where there are two assessments on day 1, one with time recorded and the other without time recorded, the one with time recorded would be selected as baseline.

- Where safety data are summarised over time, study day will be calculated in relation to date of first treatment.

Missing safety data will generally not be imputed. However, safety assessment values of the form of “< x” (i.e., below the lower limit of quantification) or > x (i.e., above the upper limit of quantification) will be imputed as “x” in the calculation of summary statistics but displayed as “< x” or “> x” in the listings. Additionally, adverse events that have missing causality (after data querying) will be assumed to be related to study drug.

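### Setting every below-limit drug concentration to missing biases the non-compartmental trough summaries upward and hides the most extreme losses of exposure

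*SAP*

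**What the plan says.** SAP 3.5.1 covers peak and trough concentrations after the first and steady-state doses and ends with the rule "Samples below the lower limit of quantification will be treated as missing in the analyses". Protocol 11.4.1 carries the same sentence, so this is not a slip in one document. The rule makes no pre-dose/post-dose distinction, and no BLQ count or sensitivity analysis is planned.

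On scale, Protocol 6.6.1 states that "The lower limit of quantification of MEDI4736 in serum is 50 ng/mL", adding that this depends on the assay. Protocol 3.2.3.2 says of the target that "100 µg/mL can be maintained with the 10 mg/kg Q2W dosing regimen".

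On antibodies, Protocol 3.2.3.2 reports that 3 of the 19 first-in-human patients tested were ADA-positive (4 of 86 samples). It describes the consequence for exposure as "with evidence for an impact on PK and target suppression in 1 individual". SAP 3.5.3 says "The effect of immunogenicity on PK, PDx, efficacy and safety will be evaluated", with any such analysis going to a separate report; SAP 4.2.7 makes it conditional on the data. Population PK (SAP 3.5.2) is also reported separately. None of these sections states how BLQ values are handled.

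For safety assessments only, SAP 4.1.3 sets values beyond a quantification limit to that limit in the summary statistics instead of dropping them.

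**The concern.** PK and immunogenicity are both secondary objectives, and the trough is one of only two PK parameters planned. Treating a result as missing is harmless if its absence says nothing about its value. Here the reason for exclusion is the value itself: the sample was taken and assayed, and the drug was too low to quantify.

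The documents anticipate a mechanism. Protocol 1.4.2 lists altered drug levels as a possible consequence of ADA, and Protocol 3.2.3.2 says the target trough was set partly to preserve exposure if ADA had an effect. The rule removes from the summary the most extreme evidence on whether that succeeded. At stake is a trough summary that looks better than the exposure patients had, with nothing in the tables to show how many results were removed.

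**Working it through.** The plan gives no BLQ rate and no figure to reproduce. The check asks whether a BLQ trough could arise by ordinary variation, which reductions in exposure the rule removes, and how far the summaries move.

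**Inputs**
- Quantification limit: 50 ng/mL = 0.05 µg/mL (Protocol 6.6.1).
- Trough: 100 µg/mL, the target in Protocol 3.2.3.2, taken as the median.
- Variability: about 50%; Protocol 3.2.3.2 says the target "accounts for the variability in PK" at that level. I read it as a coefficient of variation (CV) and also try 100%.
- Distribution: lognormal (assumption).
- f, the fraction of troughs that are BLQ at a visit: assumed, shown over a range.

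**Step 1. Could chance produce a BLQ trough?** The gap is 100/0.05 = 2000-fold, and ln(2000) = 7.60. The log-scale SD is √ln(1+CV²): 0.472 at CV 50%, 0.833 at CV 100%. The limit therefore lies 7.60/0.472 = 16 SDs below the median, or 7.60/0.833 = 9 SDs. Ordinary variability gives essentially no BLQ troughs. The PK analysis set also excludes deviations that would significantly affect PK (SAP 2.1), which largely removes missed dosing as an explanation. This applies to on-treatment troughs (pre-infusion at Weeks 8, 24 and 48, Protocol Table 1). A BLQ result before the first dose is expected and does not enter a trough summary.

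**Step 2. Which reductions are removed?** From 100 µg/mL:

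| Fall in exposure | Trough (µg/mL) | Under the rule |
|---|---|---|
| 2-fold | 50 | kept |
| 10-fold | 10 | kept |
| 100-fold | 1 | kept |
| 1000-fold | 0.1 | kept |
| more than 2000-fold | below 0.05 | dropped |

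**Step 3. How far do the summaries move?** Ratio of the summary with BLQ dropped to the summary with BLQ kept:
- Arithmetic mean, BLQ counted as 0: 1/(1−f).
- Median, BLQ ranked lowest: exp(−0.472 × z(q)), where q = (0.5−f)/(1−f) and z is the normal quantile. At f = 5%, q = 0.45/0.95 = 0.474, z = −0.066, ratio exp(0.031) = 1.03.
- Geometric mean, BLQ set to half the limit (0.025 µg/mL): (100/0.025)^f = 4000^f. Set to the limit itself: 2000^f.

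| Assumed f | Arithmetic mean | Median | Geometric mean (half the limit) | Geometric mean (the limit) |
|---|---|---|---|---|
| 1% | 1.01 | 1.006 | 1.09 | 1.08 |
| 2% | 1.02 | 1.01 | 1.18 | 1.16 |
| 5% | 1.05 | 1.03 | 1.51 | 1.46 |
| 10% | 1.11 | 1.07 | 2.29 | 2.14 |

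Every ratio exceeds 1. The median moves least. The geometric mean moves most, but its size depends heavily on the substituted constant; it is relevant because SAP 4.1 prefers geometric means for log-transformed data.

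**The case against.** The strongest reply is that the rule rarely bites. The 2000-fold gap that makes a BLQ trough informative also makes it uncommon. At f of a few percent the arithmetic mean and median shift by about 5% or less, in a descriptive summary outside the multiple testing procedure. That stands as to size. It does not answer the direction of the bias, or the lack of any count that would let a reader see whether BLQ was rare.

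A reader might infer that the rule removes the very samples that would show an ADA effect. The documents do not support that. Even a 1000-fold fall leaves a quantifiable value, so only near-complete loss of exposure disappears.

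A reader might also infer that the comparison of ADA-positive with ADA-negative patients is biased towards no effect. The sentence sits in the non-compartmental section, and the ADA-by-PK and population PK analyses are separate with no stated BLQ rule. Bias there is a risk, not a documented plan. Nor can its size be taken from the first-in-human data: Protocol 3.2.3.2 reports an effect on PK in one of three ADA-positive patients, but does not say that patient was BLQ or at what dose.

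Other outputs give partial protection. Concentrations are listed (SAP 4.2.6; Protocol 12.2.13), individual profiles are generated, and soluble PD-L1 is sampled at Day 1 and Weeks 8, 24 and 48. Abolished exposure should be traceable there, but a listing does not correct a biased summary.

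Finally, the different handling of safety values in SAP 4.1.3 is not a contradiction, because that rule is confined to safety data. It shows only that the SAP retains such values elsewhere.

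**Conclusion.** The point holds for the non-compartmental trough summaries. An on-treatment BLQ trough reflects near-complete loss of exposure, whatever its cause, and dropping it biases the summary upward. The direction is certain whenever such a trough occurs. The size is unknown because the documents give no BLQ rate. Under assumed rates of 1%, 5% and 10% the arithmetic mean is overstated by 1%, 5% and 11%, and the median by about 0.6%, 3% and 7%. The median figures also rest on a lognormal trough with CV 50%, and the 2000-fold gap on the quoted assay limit. For the ADA-by-PK and population PK analyses the finding is only that a BLQ rule is missing. The co-primary endpoints, alpha and power are unaffected.

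**What to change.** In SAP 3.5.1 and Protocol 11.4.1, replace the sentence so that:
- post-dose BLQ results are retained in the descriptive summaries, with samples from before the first dose handled separately;
- the number and percentage BLQ are tabulated by visit and by ADA status;
- medians are shown with BLQ results ranked lowest;
- if means are shown, the substituted value is stated (for example 0 or half the limit), with the BLQ-as-missing summary given as a sensitivity analysis.

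Apply the same principle to the ADA-by-PK and population PK analyses by treating BLQ observations as left-censored, and say so in SAP 3.5.2 and 3.5.3.

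This takes a few sentences and some table rows, and no new samples. Trough summaries may become slightly less favourable, and any mean will depend on the substituted value, which is why the counts and medians should carry the interpretation.
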